### 6.10.6. Febrile convulsions

- Descriptive analysis

Data about febrile convolution (definition in Section 7.2.7) within 7 days (day of vaccination and 6 subsequent days) and within 30 days (day of vaccination and 29 subsequent days) of EPI vaccine will be presented. **Separate listings** will include the diagnostic certainty level as defined in Job Aid, the duration of seizures in minutes when applicable, the time from vaccination and number of seizures.

- The IR of febrile convulsions will be computed as described in section 6.9.3.2. Of note, two at-risk periods will be considered: 0-6 and 7-29 days.

*Of note, risk period might be revised if deemed necessary at the time of the analysis.*

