8.2. Secondary objectives

In children living in the study area, prior to implementation of RTS,S/AS01_E:

- To estimate the incidence of aetiology-confirmed, and/or probable meningitis (final classification).
- To estimate the incidence of probable meningitis (final classification).
- To estimate the incidence of aetiology-confirmed, probable and/or clinically suspected meningitis (final classification).
- To monitor trends over time of meningitis cases identified at site level (first line laboratory).
- To describe risk factors for AESI, other AE leading to hospitalisation or death, meningitis and malaria.
- To describe the causes of hospitalisation (including AESI, other AE, meningitis and malaria).
- To describe the causes of death, overall and by gender.
- To assess the risk of febrile convulsions during the 7-day period and 1-month period following administration of routine EPI vaccines.
- To estimate the incidence of any malaria (including *P. falciparum* malaria) using rapid diagnostic test (RDT) and/or microscopy.
- To estimate the incidence of severe malaria (including *P. falciparum* malaria) using RDT and/or microscopy.
- To estimate the incidence of cerebral malaria (malaria diagnosed by RDT and/or microscopy).
- To estimate the prevalence of anaemia among hospitalised children.

² Acute disseminated encephalomyelitis, encephalitis, Guillain-Barre Syndrome, hypotonic hyporesponsive episode, generalised convulsive seizure.

Intussusception, hepatic failure, renal insufficiency.

Juvenile chronic arthritis, Stevens-Johnson syndrome/toxic epidermal necrolysis, Henoch-Schonlein purpura, Kawasaki disease.

Diabetes mellitus type I, thrombocytopenia, anaphylaxis.

CONFIDENTIAL115055 (EPI-MALARIA-002 VS AME)
Protocol Amendment 7 Final

- To estimate the incidence of all-cause hospitalisations and hospitalisations attributed to malaria (including *P. falciparum*).
- To estimate the mortality rate (all-cause mortality and deaths attributed to malaria [including *P. falciparum*]), overall and by gender.

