9.3.1. *Co-primary endpoints*

In children living in the study area, prior to implementation of RTS,S/AS01_E:

- Occurrence of AESI (see Section 9.2.5.1 for definition).
- Occurrence of other AE leading to hospitalisation or death (see Sections 9.2.5.2 and 9.2.5.8 for definitions).
- Occurrence of aetiology-confirmed meningitis (see Section 9.2.5.3 for case definition).

9.3.2. *Secondary endpoints*

In children living in the study area, prior to implementation of RTS,S/AS01_E:

- Occurrence of probable meningitis (final classification) (see Section 9.2.5.3 for case definition).
- Occurrence of clinically suspected meningitis (final classification) (see Section 9.2.5.3 for case definition).
- Occurrence of meningitis cases identified at site level (first line laboratory) (see Section 9.2.5.3 for case definition).
- Occurrence of hospitalisation (including those attributed to an AESI, other AE, meningitis, or malaria) or death.

CONFIDENTIAL

115055 (EPI-MALARIA-002 VS AME)
Protocol Amendment 7 Final

- Occurrence of febrile convulsions during the 7-day period (Days 0-6) and 1-month period (Days 0-29) following administration of routine EPI vaccines (see Section 9.2.5.4 for case definition).
- Occurrence of two events used as surveillance quality indicators: abscess at injection site during the 7-day period (Days 0-6) following any routine vaccination and foot positional deformation (see Section 9.2.6 for case definitions).
- Occurrence of episodes of malaria using RDT and/or microscopy
 - Any malaria (including *P. falciparum* malaria) (see Section 9.2.5.5 for case definition).
 - Severe malaria (including *P. falciparum* malaria) (see Section 9.2.5.5 for case definition).
 - Cerebral malaria (see Section 9.2.5.5 for case definition).
- Occurrence of anaemia (see Section 9.2.5.6 for case definitions) at hospital entry among hospitalised children.
- Occurrence of hospitalisation
 - All causes and hospitalisations for any malaria (including *P. falciparum* malaria), severe malaria (including *P. falciparum* malaria) and cerebral malaria (see Section 9.2.5.7 for case definitions).
- Occurrence of death
 - All causes and malaria attributed deaths (including *P. falciparum* malaria attributed death) (see Section 9.2.5.8 for case definitions).
 - AE attributed deaths (see Section 9.2.5.8 for case definitions).

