Covariates selection will be done using statistical significance. Confounders will be included in the multivariable models if univariate p-value will be less than 20%.

Co-linearity (i.e. correlation among predictor covariates) will be assessed on the full model including forced-in covariate and the other selected with the variance inflation factor (level of 10% [Hair, 1995]). If it is necessary to drop a variable due to co-linearity, the decision will be made on order of clinical importance.

Then the selected set of covariates will be entered in the final model without transformations.

- Descriptive analysis of the causes of hospitalisation (including AESI, other AE classified by MedDRA SOC and PT level, as well as meningitis and malaria) in children < 5 years will consist in computing the number of cases, person-time and incidence (with 95% CI). In the same way, descriptive analysis of causes of death classified by MedDRA will be done overall and by gender.

CONFIDENTIAL

115055 (EPI-MALARIA-002 VS AME)
Protocol Amendment 7 Final

- Incidence rate (and 95% CI) of febrile convulsions will be estimated with the same approach as for an AE. Of note, two at-risk periods will be considered: 0-6 and 7-29 days.
- Surveillance indicator analysis

The analysis done on AESI and other AE leading to hospitalisation or death will also be conducted on the incidence of foot positional deformations as a birth defect (negative control) and abscess at the injection site following routine vaccination (positive control).

The incidence rate of the negative control should not increase after the vaccination, while the increase of incidence rate of the positive control after vaccination is expected.

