### **4.2. Secondary endpoints**

As per protocol with more details.

In children living in the study area, prior to implementation of RTS,S/AS01E:

- Occurrence of probable meningitis (final classification).
- Occurrence of clinically suspected meningitis (final classification).
- Occurrence of meningitis cases identified at site level (first line laboratory):
- Occurrence of hospitalisation (including those attributed to an AESI, other AE, meningitis, or malaria) or death.
- Occurrence of febrile convulsions during the 7-day period (Days 0-6) and 1-month period (Days 0-29) following administration of routine EPI vaccine.
- Occurrence of two events used as surveillance quality indicators: abscess at injection site during the 7-day period (Days 0-6) following any routine vaccination and foot positional deformation.

In children included in AS, prior to implementation of RTS,S/AS01E:

- Occurrence of episodes of malaria diagnosed by RDT and/or microscopy
  - Any malaria
  - *P. falciparum* malaria
  - *P. vivax* or other Plasmodium species that cause malaria
  - Severe malaria
  - Severe *P. falciparum* malaria
  - Severe *P. vivax* malaria or other Plasmodium species that cause malaria
  - Cerebral malaria
  - Fatal malaria
  - Fatal *P. falciparum* malaria
- Occurrence of anaemia at hospital entry among hospitalised children
  - All anaemia
  - Severe anaemia
- Occurrence of hospitalisation
  - All causes
  - Hospitalisations for malaria (including *P. falciparum* malaria).
  - Hospitalisations for *P. falciparum* malaria
- Occurrence of death
  - All causes
  - Malaria attributed deaths
  - *P. falciparum* malaria attributed deaths
  - AE attributed deaths

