#### **6.9.3.2. Incidence following EPI vaccine or virtual vaccination**

Analyses of incidence following EPI vaccine or virtual vaccination will only be performed on children enrolled in the AS ATP cohort for each group (6-12 weeks and 5-17 months).

These analyses will be computed on each confirmed co-primary endpoints (see section 6.9.2) by dividing the number of study participants reporting at least one event over the

follow-up period by the total person-time. A 95% CI will be computed using an exact method for a Poisson variable. Incidence per 100,000 person-years will be presented by study sites and overall.

Incidence Rates (IRs) after the primary schedule (i.e. combining the 3 doses) and the virtual secondary schedule (i.e. primary schedule and the virtual dose 4) will be presented.

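### Febrile convulsions: the endpoint windows are Days 0-6 and Days 0-29, but incidence rates are planned only for Days 0-6 and 7-29, so the 1-month window has no committed rate or confidence interval

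*SAP*

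**What the plan says.** The secondary objective in protocol 8.2 is "To assess the risk of febrile convulsions during the 7-day period and 1-month period following administration of routine EPI vaccines". Protocol 9.3.2 fixes the windows: "Occurrence of febrile convulsions during the 7-day period (Days 0-6) and 1-month period (Days 0-29) following administration of routine EPI vaccines". SAP 4.2 repeats them.

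The analysis text uses a different pair. Protocol 9.7.6.2 reads "Of note, two at-risk periods will be considered: 0-6 and 7-29 days", and SAP 6.10.6 carries this over: "two at-risk periods will be considered: 0-6 and 7-29 days". The rate itself follows SAP 6.9.3.2, where "A 95% CI will be computed using an exact method for a Poisson variable".

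SAP 6.10.6 also has a descriptive part. Data within 7 days and "within 30 days (day of vaccination and 29 subsequent days) of EPI vaccine will be presented", with listings that include time from vaccination. The section closes with "Of note, risk period might be revised if deemed necessary at the time of the analysis".

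SAP Table 5 marks febrile convulsions for description of events and for incidence following the primary and secondary schedules. It does not mark them for cumulative probability.

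**The concern.** The endpoint windows are nested: the 1-month window starts at Day 0 and contains the first week. The rate windows are disjoint. Days 0-6 appears in both sets. Days 0-29 appears in the endpoint and the description but not among the rates, and Days 7-29 is not an endpoint window at all.

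One of the two stated windows therefore has no person-time rate and no interval committed. The background in protocol 7.2 reports the Phase III evidence on febrile convulsions over 7 days and over 30 days after vaccination. This study is meant to supply baseline figures for EPI-MAL-003, with aligned endpoints (protocol 9.3). A 30-day rate is the natural baseline quantity, and as written the reader would have to assemble it.

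Assembling it needs a rule for a child who has a convulsion on Days 0-6. The SAP does not say explicitly whether that child leaves follow-up for that dose or enters the 7-29 window still at risk.

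**Working it through.** **Windows side by side**

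| Source | First window | Second window | Output |
|---|---|---|---|
| Protocol 9.3.2, SAP 4.2 (endpoint) | Days 0-6 | Days 0-29 | – |
| SAP 6.10.6, descriptive part | 7 days | 30 days | Description, listings |
| Protocol 9.7.6.2, SAP 6.10.6 (rate) | Days 0-6 | Days 7-29 | Rate, exact 95% CI |

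**Does anything else supply a Days 0-29 estimate?** Table 5 plans no cumulative probability for febrile convulsions, so no Kaplan-Meier figure at Day 29 fills the gap. The closing sentence of SAP 6.10.6 allows a revision but commits to none.

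**Is pooling defined?** SAP 6.9.3.2 contains three relevant rules:

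- Follow-up stops at the first occurrence after a given dose.
- Events outside the at-risk period, before or after, are censored.
- Table 2 starts every follow-up period at the reference date.

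The first rule suggests that a child with a Day 0-6 event is finished for that dose. The second can be read as ignoring that event when the 7-29 window is analysed. The third gives no start rule for a window that opens on Day 7.

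**Check of the rate method.** The documents give no expected rate or precision for febrile convulsions, so there is no such figure to reproduce. Events divided by person-years, with exact Poisson limits, does reproduce protocol Table 6:

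- 2-week row: 10,000 × 4 × 2/52 = 1538.46 PY; 1 event gives 65.0 [1.6, 362.2] per 100,000 PY.
- 6-week row: 10,000 × (2/12 + 2 × 6/52) = 3974.36 PY; 1 event gives 25.2 [0.6, 140.2].

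**Person-time for these windows.** Inputs are 10,000 children per group (protocol 9.5), doses usually at 6, 10 and 14 weeks, so 28 days apart (SAP 6.8), and censoring at the next dose (SAP 6.9.3.2). Days at risk per child over three doses, before any loss to events or dropout:

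- Days 0-6: 7 + 7 + 7 = 21, giving 10,000 × 21/365.25 = 574.9 PY.
- Days 7-29: 21 + 21 + 23 = 65, giving 1779.6 PY.
- Days 0-29: 28 + 28 + 30 = 86, giving 2354.6 PY, the sum of the two apart from rounding.

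With doses at least 30 days apart, Days 0-29 would give 90 days, or 2464.1 PY. The 4-week schedule thus delivers 86/90 = 96% of the nominal time, and all of the loss is after doses 1 and 2.

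**Illustration with assumed counts.** Take 17 events on Days 0-6 and 63 on Days 7-29. These are assumptions, set near the Phase III control figures in protocol 7.2 for children aged 5-17 months: 0.57 per 1000 doses × 30,000 doses ≈ 17, and 0.8% × 10,000 = 80 over 30 days, leaving 63. They are not expectations for this study.

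| Window | Events | Rate per 100,000 PY | 95% CI |
|---|---|---|---|
| Days 0-6 | 17 | 2956.8 | 1722.4 to 4734.1 |
| Days 7-29 | 63 | 3540.1 | 2720.3 to 4529.3 |
| Days 0-29, no child in both windows | 80 | 3397.7 | 2694.1 to 4228.7 |
| Days 0-29, 5 children in both windows | 75 | 3185.3 | 2505.5 to 3992.8 |

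The pooled figure (d1 + d2)/(PY1 + PY2) equals the first-event Days 0-29 rate only when no child has an event in both windows after the same dose. Five such children change it by 5/80 = 6%.

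**The case against.** The strongest reply is that little is lost. SAP 6.10.6 does present data within 30 days. SAP section 6 makes frequency and percentage the default for categorical variables and leaves room for confidence intervals in the separate table shells. The objective speaks of assessing risk, and a percentage with an event within 30 days is a risk. Days 0-6, where the identified risk lies, has its own rate and exact interval. Disjoint windows have a merit too: a 7-29 rate shows whether any excess is confined to the first week, which a pooled rate dilutes. On the natural reading of the first-occurrence rule the two windows simply add, and no child is counted twice. Finally, the identified risk belongs to RTS,S/AS01E, which is not given in this baseline study.

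Much of this stands, and it limits the point. It does not supply a committed rate or interval for Days 0-29: the text makes intervals in the tables optional, and the sentence on revising the risk period leaves the choice to the time of analysis. The additive reading is plausible but is inferred from a rule written for windows that start at the dose.

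A reader might infer three stronger things that the documents do not support:

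- **That the 1-month risk goes unexamined.** It is described over the correct window.
- **That the 7-29 rate serves as the 1-month rate and so drops 7 of 30 days (23%), including the week of concern.** Neither document gives 7-29 that role, and those days have their own rate. The 23% is a share of days, not a bias.
- **That the SAP departs from the protocol.** Protocol 9.7.6.2 has the same windows. The mismatch is with the endpoint, in both documents.

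**Conclusion.** Wrong as written: the planned rate windows do not match the stated endpoint. Days 0-6 is properly covered. Days 0-29 has a descriptive presentation but no committed incidence rate or interval, and the handling of a Day 0-6 event in the 7-29 window is not explicit.

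The size is one missing estimate for one secondary endpoint. No planned figure is biased by it. If the first-occurrence rule applies across both windows, the 1-month rate can be recovered exactly from the tabulated events and person-time. Otherwise the pooled figure is off by the share of children counted twice, which is 6% if 5 of 80 assumed events are repeats. That illustration rests on assumed counts, full follow-up of 10,000 children and doses exactly 28 days apart. The mismatch itself rests only on the text.

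**What to change.** In SAP 6.10.6, add an at-risk period of Days 0-29, counting the first event per dose and stopping follow-up at the event or the next dose, with the other stops of Table 2. Keep Days 7-29 as supplementary and state its rule. One consistent choice is that a child with an event on Days 0-6 contributes no further events or time for that dose, so the two sub-windows add up to Days 0-29.

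State that with doses usually 4 weeks apart the window ends at about 28 days after doses 1 and 2, and report the person-time actually accrued. Record the added window in SAP section 9 as a difference from protocol 9.7.6.2.

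The cost is small: no new data, one more window in an analysis already run for two, the matching table columns and an entry in section 9. For other adverse events, SAP 6.9.3.2 already applies at-risk periods of 7 and 30 days, so the approach is already in the plan.

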### 6.10.7. Surveillance indicator analysis

*This analysis will be done only in children enrolled in AS.*

*Abscess at the injection site (positive control), reported during outpatient visits and at hospital within 7 days of EPI vaccine will be described.*

The prevalence of Foot positional deformations as a birth defect (negative control) reported during outpatient visits and at hospital, will be computed.

Abscess at the injection site and foot positional deformations reported during home visits will only be described.

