## 6.8. Exposure description to EPI vaccines

EPI vaccines are those routine vaccines usually given at 6, 10 and 14 weeks of age and which could be DTP, DTP-HepB, DTP-HepB-Hib vaccine. The subjects who received at least one dose of EPI vaccine are the vaccinated subjects.

The coding of vaccine is under the Epidemiologist team (EPI) responsibility (See details described in specific guideline: [Vaccine study-specific Coding Guidelines](#)).

The number of subjects who received at least one EPI dose will be described according to study group as well as the number of doses, the source for vaccine history (i.e. individual vaccination cards, vaccination registers at the health care facilities and vaccination data collected during census rounds).

Moreover, the age at each dose administration and the time between doses will also be described using descriptive statistics.

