- The percentage of subjects reporting abscess at injection site within 7 days (day of vaccination and 6 subsequent days) after each dose of the DTP/HepB/Hib vaccine will be reported for each dose and overall according to gender and overall.
- As negative control, the prevalence of foot positional deformations will be presented according to gender and overall.

Of note, each progress report will be done on uncleaned data and will present cumulative results. The same analysis will be performed for the interim analysis on cumulative cleaned data. ***The final analysis will be done only on confirmed cases according to the protocol case definitions.***

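### The positive-control abscess endpoint covers any routine vaccination, but the SAP's facility-based analysis covers only DTP-based doses, which leaves on-schedule catch-up children without a prospectively observed window

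*SAP*

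**What the plan says.** **Endpoint.** Protocol 9.3.2 lists as a surveillance quality indicator "abscess at injection site during the 7-day period (Days 0-6) following any routine vaccination". SAP 4.2 keeps that scope: abscess at "injection site during the 7-day period (Days 0-6) following any routine vaccination and foot positional deformation". Protocol 9.2.6 and 9.7.6.2 also tie the positive control to routine vaccination, without naming a product.

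**Analysis.** SAP 6.10.7, which is limited to active surveillance, states that abscesses "reported during outpatient visits and at hospital within 7 days of EPI vaccine will be described". SAP 6.8 says which vaccines that means: those "usually given at 6, 10 and 14 weeks of age and which could be DTP, DTP-HepB, DTP-HepB-Hib vaccine". SAP 6.9.3.1 leaves no doubt. It plans the percentage of subjects with an abscess "within 7 days (day of vaccination and 6 subsequent days) after each dose of the DTP/HepB/Hib vaccine", and carries the progress-report tables into the final report. The last sentence of SAP 6.10.7 adds that abscesses reported at home visits will be described; it gives neither a vaccine nor a time window.

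**Declaration.** SAP section 9 (Changes from protocol) does not mention a narrower vaccine scope. For section 6.10.7, the Amendment 2 entry in the SAP document history records only the removal of the incidence rate and the restriction to active surveillance.

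**The concern.** The SAP states one endpoint and analyses another. An abscess after a routine injection given on a date away from any DTP dose meets the endpoint in Protocol 9.3.2 and SAP 4.2, but falls outside the outpatient and hospital analysis.

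The loss is uneven across subgroups. Children in the 6-12 weeks group and the 5-17 months first-DTP subgroup are enrolled at or around their first DTP dose, so they have real DTP windows. Catch-up children enrol at 5 to <18 months, after the usual DTP series should be complete.

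What is at stake is the use of the indicator. Protocol 9.1.1 includes it to assess changes in how well the health care system diagnoses disease, and Protocol 9.9 relies on it to detect trends in surveillance capacity. Only the 5-17 months age group is kept in EPI-MAL-003 (Protocol 7.1), and its home visits start at about 6 months (first-DTP) or at first contact (catch-up). With on-time dosing, facility-based abscess detection is tested before those ages and hardly at all within them.

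A related gap is that SAP 6.9.3.1 does not state the denominator of its percentage. Vaccination history comes partly from cards and registers (Protocol 9.3.3.1), so DTP doses given before enrolment may be on file for catch-up children. If those doses enter the denominator, unobserved windows would dilute the percentage.

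**Working it through.** This is mainly a comparison of definitions. The arithmetic serves to size the subgroup and to test whether its windows can be observed.

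**Subgroup size** (Protocol 9.2.1.1 and 9.5)
- The 5-17 months target is 15,000 and the expected first-DTP number is 6,375. Then 15,000 - 6,375 = 8,625, which reproduces the catch-up number in the protocol.
- Share of the 5-17 months group: 8,625 / 15,000 = 57.5%.
- These are planned numbers. About 10,000 per group are analysed, because the Burkina Faso sites are excluded. If the planned split carried over (an assumption), catch-up would be 0.575 × 10,000 = 5,750.

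**Last countable day after an on-time third dose**
- The third dose is usually given at 14 weeks, which is day 98. Days 0-6 then end on day 98 + 6 = 104 (14.9 weeks).

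**First day of observation for a catch-up child**
- The youngest enrolment age is 5 months (Protocol 9.1), and facility visits are recorded from enrolment (Protocol 9.2.7.1.8).
- With a month of 365.25 / 12 = 30.44 days, 5 months is day 152.
- The gap is 152 - 104 = 48 days, or about 6.9 weeks. Even the youngest catch-up child, if vaccinated on schedule, enters after the last DTP window has closed.

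**How late a third dose must be for any part of its window to be observed**

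The dose must fall no earlier than 6 days before enrolment, so the delay in weeks is (enrolment day - 6 - 98) / 7:

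| Age at enrolment | Day | Delay against week 14 |
|---|---|---|
| 5 months | 152.2 | 6.9 weeks |
| 8 months | 243.5 | 19.9 weeks |
| 11.5 months (middle of the range) | 350.0 | 35.1 weeks |

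**What cannot be computed.** The documents give no dose counts for other routine vaccines, no frequency of late DTP doses and no abscess rate. The share of eligible windows or abscesses lost therefore cannot be stated.

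**The case against.** The strongest reply is that a DTP anchor already exists in the protocol. Protocol 9.7.6.2 says the AESI analysis will also be applied to abscess, and Protocol 9.7.5.2.1 anchors that analysis on DTP/HepB/Hib or virtual vaccination. The Annex 3 glossary describes the national EPI by the 6, 10 and 14 week schedule, with DTP/HepB/Hib as the example. This shows how the narrowing may have arisen, but it does not settle the matter. Protocol 9.7.6.2 itself speaks of abscess following routine vaccination, the glossary gives DTP only as an example, and both endpoint lists say any routine vaccination. Elsewhere the protocol uses EPI more widely: BCG in 9.4.1, and measles and yellow fever in 7.2. The 7.2 mention concerns the Phase III trial, so it bears on the meaning of the term and not on the schedule at these sites.

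Three other points stand and limit the finding:

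- A reader might infer that catch-up children have no countable window at all. The documents do not support that. Late DTP doses are foreseen (Protocol 9.2.1.1 and 9.2.7.1), and abscess is recorded at home visits V1 to V9 (Protocol Table 4).
- A reader might infer that abscesses at other vaccines' injection sites are dropped. The rule is a time window and not a site rule, so an abscess at another site within 7 days of a DTP dose still counts.
- A reader might infer that the indicator is silent on detection after about four months of age. Late doses and the home-visit description prevent that reading.

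It is also fair to say that no co-primary incidence rate depends on this descriptive indicator, that Amendment 2 aimed to lighten the outputs, and that Protocol 9.3 aligns endpoints with EPI-MAL-003, whose protocol is not available here. These are reasons to keep a DTP-only row. They do not justify leaving the stated endpoint unanalysed.

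**Conclusion.** The mismatch is real and undeclared. Followed as written, the SAP does not analyse the positive-control endpoint that it states. Facility-reported abscesses after routine injections on non-DTP dates are excluded, and on-schedule catch-up children contribute no prospectively observed window. The catch-up subgroup is 57.5% of the planned 5-17 months group; how many of its members had a late DTP dose is not known from the documents. The timing result assumes the usual 6, 10 and 14 week schedule and observation from enrolment.

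This should be corrected, but it concerns the interpretation of a secondary quality indicator. It does not alter any co-primary estimate.

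**What to change.** In SAP 6.10.7 and 6.9.3.1:

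1. Count abscesses on Days 0-6 after any recorded routine injectable vaccination given under observation, that is, after enrolment.
2. Keep the DTP-only result as a separate row, for continuity with the progress reports and the interim analysis.
3. Report the number of evaluable vaccination dates separately for the 6-12 weeks group, the 5-17 months first-DTP subgroup and the catch-up subgroup, and use them as the denominator.
4. State how the first DTP dose is handled when consent follows it, since SAP 5.2 allows up to 10 days. SAP 6.9.3.2 already starts follow-up at consent in that situation, and the same rule would serve here.

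If the sponsor prefers to stay with DTP doses only, the least that is needed is to declare and justify the restriction in SAP section 9 and to give the evaluable dates by subgroup.

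The cost is a little extra programming and a few more output rows. No new data are needed, because all immunisations are already recorded with type and date (Protocol 9.2.7.1.6 and Table 4).
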